7.0 DATA COLLECTION AND SAFETY MONITORING

Pre-therapy evaluation data, as detailed above, radiation therapy treatment data, as well as the results of post-therapy exams and imaging studies will be collected by the Office of Clinical Research at DHMC, and reviewed quarterly by the Principal Investigator ([name]). The NCCC Safety and Data Monitoring Committee will also monitor this protocol on a quarterly basis.

8.0 STATISTICAL CONSIDERATIONS

The primary objective of this study is to evaluate the in-breast recurrence rate of borderline and malignant phyllodes tumors treated with breast conserving resection and adjuvant partial breast radiation therapy. Based on our literature review, the in-breast recurrence rate after margin negative breast conserving resection alone is approximately 21 percent. A clinically meaningful improvement for the experimental therapy would be an in-breast recurrence rate of 5 percent or less.

The secondary objective is to compare the local recurrence rate observed after partial breast radiation therapy with that observed in historical controls treated with whole breast radiation therapy after breast conserving resection with negative margins (study DMS 9801, ref 5). This recurrence rate was zero (0/46 patients).

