New methods for delivering breast radiotherapy are being developed that allow radiation to be delivered solely to the area of the surgical resection site, termed partial breast radiation. The main advantage of partial breast radiation is that it simplifies treatment for the patient: radiation is delivered twice a day for 5 days, rather than 5 days per week for 6 weeks. The main concern is that partial breast irradiation might miss other sites of breast cancer in the ipsilateral breast. This is a significant concern for patients with invasive ductal or lobular carcinoma, where multicentric tumors may be present in 5 to 10% of patients. This concern was lessened by data from the NSABP-06 study, where patients were randomized to receive lumpectomy or lumpectomy plus radiation therapy. In this study the development of tumors "elsewhere" in the ipsilateral breast (away from the primary tumor site) was the same (3%) whether or not the patient received adjuvant radiation therapy (14). Indeed, evidence is accumulating from prospective studies that adjuvant partial breast irradiation after resection of invasive adenocarcinoma of the breast results in rates of local recurrence that are comparable to those seen after whole breast radiation therapy. The study with the longest follow-up utilized several brachytherapy catheters to radiate just the area around the surgical resection site in 120 patients undergoing breast conserving surgery (15). The local recurrence rate at 5 years was 1%, which is comparable to that achieved in patients undergoing whole breast radiation. The Mammosite® catheter has simplified the delivery of partial breast radiotherapy. This is a balloon catheter which can be easily inserted in the cavity left after breast conserving surgery. A radioactive source is placed in the center of the balloon to deliver radiation. A large registry of 1440 patients treated with partial breast radiation indicates that at 3 years of follow-up the local recurrence rate after breast conserving surgery and Mammosite® brachytherapy is very low: 1.6% (16). An alternative method of partial breast radiotherapy which is gaining in popularity is external beam partial breast radiation therapy. This technique does not require placement of a balloon catheter in the breast, but relies on careful dosimetry to focus external beam radiation to the area around the surgical site. Although there is only short follow-up data available for patients treated with external beam PBI, this technique has been used for greater than 70% of women treated with PBI on the NSABP B-39 protocol. Both Mammosite® and external beam partial breast radiation

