2.0 OBJECTIVES

- 2.1 The primary objective is to determine the local recurrence rate for patients with borderline or malignant phyllodes tumors treated with breast conserving resection with negative margins and adjuvant partial breast radiation therapy.
- 2.2 The secondary objective is to compare the local recurrence rate observed after partial breast radiation therapy with that observed in historical controls treated with whole breast radiation therapy after breast conserving resection with negative margins (study DMS 9801, ref 5).
- 2.3 Additional secondary objectives will be to observe the incidence of tumor development elsewhere in the breast and the rate of distant metastases.

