8.1 Statistical analysis

The rate of in-breast recurrence will be calculated with an exact binomial confidence interval. A binomial test (i.e., one sample proportion test) will be used to compare this rate to the rate of 21% determined from the literature for margin negative breast conserving resection alone. To address the secondary aim the rate from this study will be compared to the rate (0/46) obtained in the study using adjuvant whole breast radiation using a Fisher's exact test.

Additional analysis will include descriptive summaries of adverse events, time to recurrence and survival. Time to recurrence and survival will be estimated separately for the borderline and malignant tumor groups using the product limit method.

Sample Size and Power Considerations

A total sample of 50 patients will be enrolled and followed for recurrence. This yields sufficient power (i.e., 80%) to detect that adjuvant partial breast radiation is better than margin negative breast conserving resection alone, if indeed this adjuvant therapy reduces the rate to 6% or less, and the rate with resection alone is 21%. This calculation sets the type I error rate (α) at the usual 0.05. The 95% exact binomial confidence interval has an expected range of 1% to 15% if the actual rate is 5% (whereas it is 0% to 8% if the actual rate is 1%, and it is 4% to 22% if the actual rate is 10%). In comparison to the adjuvant whole breast radiation in which our prior study found no in-breast recurrences in 46 women, partial breast radiation will be identified as having a significantly higher rate if its actual rate is 15% or higher (assuming an α =0.5, and use of a Fisher exact test).

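### Does naming the primary endpoint local recurrence in Section 2 and in-breast recurrence in Section 8 leave the primary result open?

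*Combined protocol and SAP*

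**What the plan says.** Section 2.1 gives the primary objective as to "determine the local recurrence rate for patients with borderline or malignant phyllodes tumors". Section 2.2 uses the same term for the comparison with the whole-breast radiation study. Section 2.3 adds, as a further secondary objective, to "observe the incidence of tumor development elsewhere in the breast and the rate of distant metastases".

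Section 8.0 restates the primary objective as to "evaluate the in-breast recurrence rate of borderline and malignant phyllodes tumors", and sets the benchmark by saying that "the in-breast recurrence rate after margin negative breast conserving resection alone is approximately 21 percent". Section 8.1 carries that wording into the analysis: "The rate of in-breast recurrence will be calculated with an exact binomial confidence interval", and then "A binomial test (i.e., one sample proportion test) will be used to compare this rate to the rate of 21" percent. The historical comparison in 8.1 takes the rate from this study, without a new definition, and sets it against 0/46 by Fisher's exact test.

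No section defines either term by location. Section 6.0 asks for prompt reporting of biopsy-proven phyllodes recurrences and sets no location criterion.

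**The concern.** Read literally, the two sections could sort the same event differently. A phyllodes tumor in the treated breast, away from the resection site, looks secondary under Section 2 because 2.3 lists it separately. It looks primary under Section 8 because it is in the breast. Section 1.0 also says of the technique: "The main concern is that partial breast irradiation might miss other sites of breast cancer in the ipsilateral breast".

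If the narrow reading were adopted, failure outside the irradiated volume could not affect the primary verdict. The trial expects few events, so one reclassified patient could decide whether the result differs significantly from 21%. The study has a single arm and the Principal Investigator reviews outcomes quarterly (Section 7.0), so an open definition might be settled after the data are known.

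**Working it through.** **1. How the document uses the two terms.**

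| Item | Called local | Called in-breast |
|---|---|---|
| 21% after resection alone | Section 1.0, literature review | Section 8.0 |
| 0/46 after whole-breast radiation | Section 1.0, account of DMS 9801 | Section 8.1, sample size paragraph |
| Primary objective | Section 2.1 | Sections 8.0 and 8.1 |

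The same figures carry both labels. The Introduction also uses both terms in one sentence about the consequences of recurrence. Criterion 3.13 admits a patient with a local recurrence only if it lies in the area of the earlier excision. That condition would be unnecessary if local already meant the resection site. The table and the criterion point to one endpoint with two names.

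**2. The plan's power figure.** Inputs from Section 8.1: n = 50, null rate 21%, alternative 6%, α = 0.05. Sidedness and cutoff are not stated. With X the number of events,

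P(X ≤ c) = Σ (x = 0 to c) C(50, x) pˣ (1 − p)⁵⁰⁻ˣ.

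- Two-sided exact test: the largest significant count below 21% is c = 4. Power at 6% is P(X ≤ 4) = 82.1%. Power is exactly 80% at a true rate of 6.24%, which rounds to the stated 6%.
- One-sided exact test: c = 5, and power at 6% is 92.2%.

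The two-sided test is the closer match to the stated 80% and is used below, with the one-sided result beside it.

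**3. Sensitivity at the boundary.**

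| Events in 50 | Two-sided p against 21% | One-sided p | 95% exact CI | Fisher p against 0/46 |
|---|---|---|---|---|
| 4 | 0.023 | 0.012 | 2.2% to 19.2% | 0.118 |
| 5 | 0.057 | 0.034 | 3.3% to 21.8% | 0.057 |
| 6 | 0.163 | 0.076 | 4.5% to 24.3% | 0.027 |

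A single elsewhere event changes the primary verdict only when there are exactly 4 site events (two-sided) or exactly 5 (one-sided). At a true site rate of 6% these counts have probability 17.3% and 10.2%. For the Fisher comparison at α = 0.05 the critical count is exactly 5 site events, again 10.2%. In each case an elsewhere phyllodes event must occur as well.

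**4. Chance that the two readings disagree.** Let s be the site rate and e the rate of phyllodes tumor elsewhere, each patient counted once. The broad count is never below the narrow count. So the verdicts differ only when the narrow count passes and the broad count fails:

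P(disagree) = P(X ≤ c; s) − P(X ≤ c; s + e).

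The plan gives no value of e for phyllodes tumors, so the values below are assumptions. With s = 6%:

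| Assumed e | Two-sided, c = 4 | One-sided, c = 5 |
|---|---|---|
| 0.25% | 82.1 − 79.9 = 2.2% | 92.2 − 91.0 = 1.3% (unrounded inputs) |
| 0.5% | 82.1 − 77.6 = 4.4% (unrounded inputs) | 92.2 − 89.6 = 2.7% (unrounded inputs) |
| 1% | 82.1 − 72.9 = 9.2% | 92.2 − 86.5 = 5.7% |

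With s = 3% and c = 4, the first two rows become 0.6% and 1.3%.

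**5. What the plan says about e.** Section 1.0 calls multicentric phyllodes tumors very rare and reports that all 37 recurrences in its literature review were at the resection site, that is, 0 of 37 elsewhere.

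**The case for a change.** The best case for a change is that treating the terms as synonyms does not dispose of Section 2.3. By listing tumor elsewhere in the breast separately, the plan invites the reading that such tumors are not primary events, and no sentence says otherwise. The fix would be cheap, a matter of wording in four places. Nor do the literature data prove that elsewhere disease is negligible. Zero elsewhere recurrences in the 124 patients cited has a one-sided 95% upper limit of 1 − 0.05^(1/124) = 2.4%. An elsewhere rate of 2% would make the two readings disagree with probability 82.1 − 62.9 = 19.2% (two-sided test, 6% site rate).

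Part of this stands. The location of a primary event is never written down, and a short definition would be tidier. Three points limit its force.

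- Section 2.3 can be read as reporting location alongside the primary rate. It also speaks of tumor development rather than recurrence, so it may cover new tumors of any histology.
- Section 8.1 governs the test and names in-breast recurrence. Counting every phyllodes recurrence in the ipsilateral breast is the plain reading. It can only add events, so it never favors the treatment, and an analyst who dropped an elsewhere recurrence would be departing from that text.
- The sentence in Section 1.0 about missed sites concerns invasive ductal or lobular carcinoma. Section 1.0 says later data lessened that concern, then contrasts phyllodes tumors as very rarely multicentric. A new carcinoma would not be a phyllodes recurrence in any case, so the 3% elsewhere figure for invasive cancer is not a fair value for e.

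**Conclusion.** The wording differs, and the p-values and intervals behind the concern are correct, but no change to the plan follows. This is a missing definition that the analysis section already fills sensibly: the tested variable is phyllodes recurrence in the breast, and an analyst following Section 8.1 reaches a sound result. Adding the definition would leave the sample size, the test and the 21% benchmark as they are.

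This conclusion rests mainly on the text: both key figures carry both labels, criterion 3.13 qualifies the word local, and Section 8.1 names what is tested. The size of the effect is secondary. At a 6% site rate and with the two-sided test, the readings would disagree with probability of about 2% to 4% for an elsewhere rate of 0.25% to 0.5%, and about 9% for 1%. Those elsewhere rates are assumed, and a materially higher rate would make the ambiguity matter more. The two-sided test is inferred from the stated power; if the test is one-sided, the boundary moves from 4 versus 5 events to 5 versus 6 and the probabilities fall.

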8.1 Statistical analysis

The rate of in-breast recurrence will be calculated with an exact binomial confidence interval. A binomial test (i.e., one sample proportion test) will be used to compare this rate to the rate of 21% determined from the literature for margin negative breast conserving resection alone. To address the secondary aim the rate from this study will be compared to the rate (0/46) obtained in the study using adjuvant whole breast radiation using a Fisher's exact test.

Additional analysis will include descriptive summaries of adverse events, time to recurrence and survival. Time to recurrence and survival will be estimated separately for the borderline and malignant tumor groups using the product limit method.

Sample Size and Power Considerations

A total sample of 50 patients will be enrolled and followed for recurrence. This yields sufficient power (i.e., 80%) to detect that adjuvant partial breast radiation is better than margin negative breast conserving resection alone, if indeed this adjuvant therapy reduces the rate to 6% or less, and the rate with resection alone is 21%. This calculation sets the type I error rate (α) at the usual 0.05. The 95% exact binomial confidence interval has an expected range of 1% to 15% if the actual rate is 5% (whereas it is 0% to 8% if the actual rate is 1%, and it is 4% to 22% if the actual rate is 10%). In comparison to the adjuvant whole breast radiation in which our prior study found no in-breast recurrences in 46 women, partial breast radiation will be identified as having a significantly higher rate if its actual rate is 15% or higher (assuming an α =0.5, and use of a Fisher exact test).

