In 1998 we initiated a prospective single arm study (DMS 9801) to determine whether adjuvant radiation therapy after breast conserving resection of borderline and malignant

phyllodes tumors decreases the local recurrence rate (5). Forty six women were treated at 30 different institutions. The mean patient age was 49 years (18-76). Thirty patients (65%) had malignant phyllodes tumors, the rest were borderline malignant. The mean tumor diameter was 3.7 cm (0.8-11 cm). Eighteen patients had a negative margin on the first excision. The median size of the negative margin was 0.35 cm (range <0.1-2 cm). Twenty eight patients underwent a re-excision because of positive margins in the initial resection. Two patients died of metastatic phyllodes tumors. With a median follow-up of 56 months (range 12-129 months), none of the 46 patients developed a local recurrence (local recurrence rate zero (95% CI 0 - 8%)). We concluded that adjuvant radiation therapy decreased the local recurrence rate after breast conserving resections of phyllodes tumors.

A recent retrospective report from the Rare Cancer Network also provides strong support for the use of adjuvant radiation therapy after resection of phyllodes tumors (4). Of 159 patients with borderline or malignant phyllodes tumors, 109 were treated with breast conserving surgery and 50 underwent mastectomy. Thirty six received adjuvant radiation therapy. When all 159 patients were considered the percentage free of local recurrence at 10 years in the group that received radiation therapy was significantly better than the group that did not receive radiation therapy (86% vs 59%, p= 0.02). Of the 109 patients treated with breast conserving surgery, 11 underwent radiation therapy and 68% were free of local recurrence at 10 years compared to 54% of the 98 patients who underwent lumpectomy without radiation therapy. Of the 50 mastectomy patients, 25 underwent radiation therapy and 92% were free of local recurrence at 10 years, compared to 78% of the patients undergoing mastectomy without radiation therapy. While the trends in each of these subgroups favor radiation therapy, the differences were not statistically significant. In multivariate analysis the only favorable independent prognostic factor was the use of radiation therapy.

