
therapy are currently being compared to whole breast radiation therapy in the prospective randomized study, NSABP-B39.

In contrast to patients with invasive carcinomas of the breast, it is very rare for patients to have multicentric phyllodes tumors. In our literature review all 37 recurrences seen in the 124 patients that had undergone margin negative breast conserving resections were at the site of the initial tumor resection. Therefore we hypothesize that adjuvant partial breast irradiation is likely to be as effective as whole breast radiation therapy after resection of malignant phyllodes tumors.

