9.0 RISK/BENEFIT STATEMENT

In an effort to decrease the local recurrence rate, while preserving the breast, we propose adding adjuvant radiation therapy to local excision. Partial breast radiation, if as effective as whole breast radiation therapy, is preferable for many patients because the duration of treatment is much shorter (5 days vs 6 weeks).

The risks of surgery plus external beam partial breast radiation therapy are:

- 1. Effects in 10% or more of patients: reddening of the skin during treatment and for several weeks following treatment, tanning of the breast skin which may be permanent, slightly smaller breast size or change in the way the breast looks, tiredness and weakness during treatment and for several weeks following treatment.
- 2. Effects in 3-9% of patients: peeling of the skin in the area treated with radiation, pain at the site of radiation.
- 3. Effects in < 1% of patients: cough, difficulty breathing, pericarditis, myocarditis, rib fracture.

Although there is a well documented risk of malignancy associated with exposure to radiation, we have searched the literature and are unaware of any studies which have demonstrated an increased risk of second malignancies in patients who have been treated with whole breast radiation therapy after breast conserving surgery. One study demonstrated that patients treated with whole breast radiation therapy did not have a significantly higher incidence of leukemia than patients treated with breast conserving surgery alone (18).

There is no evidence that treatment on this protocol will result in decreased survival from phyllodes tumors, even if the adjuvant radiation therapy is completely ineffective.

The benefits of being enrolled in this study are that the women will be treated with breast conservation, rather than mastectomy, and that they will receive adjuvant radiation therapy in a much shorter time frame than they would have if they were to receive whole breast radiation therapy.

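### The only planned comparison with whole breast radiation is a Fisher test for a difference from 0/46, which cannot support the protocol's hypothesis that partial breast radiation is as effective

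*Combined protocol and SAP*

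**What the plan says.** Section 1.0 ends with the hypothesis that "adjuvant partial breast irradiation is likely to be as effective as whole breast radiation therapy after resection of malignant phyllodes tumors". Section 9.0 makes the case for the shorter treatment conditional on the same idea: "Partial breast radiation, if as effective as whole breast radiation therapy, is preferable for many patients".

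The objective built on this (section 2.0) is worded neutrally: "The secondary objective is to compare the local recurrence rate observed after partial breast radiation therapy with that observed in historical controls". Those controls are the DMS 9801 patients, who received whole breast radiation. That study had no local recurrence in 46 patients, and section 1.0 gives the 95% confidence interval as 0 to 8%.

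Section 8.1 states the analysis in one sentence: "the rate from this study will be compared to the rate (0/46) obtained in the study using adjuvant whole breast radiation", by Fisher's exact test. The sample size paragraph adds that, with 50 patients, a significantly higher rate will be identified if the true rate is 15% or more. For this test it prints α as 0.5. Sidedness is not stated. The plan gives no margin, no interval for the difference and no rule for reading a non-significant result.

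**The concern.** The hypothesis is one of similar efficacy, and the test looks for a difference. With zero events in the control group, partial breast radiation cannot be shown better. It is either significantly worse or not shown to differ, and failing to show a difference between groups of 50 and 46 with very few events is weak evidence that they are alike.

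What is at stake is how the result will be reported. Some outcomes would pass the primary test against 21% and also give a non-significant comparison with whole breast radiation. Nothing in the plan would stop that pair of results from being presented as confirming the section 1.0 hypothesis, even where the data leave room for a large excess of recurrences.

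**Working it through.** **Inputs.** Partial breast group n = 50 (8.1). Control 0/46 (8.0). Resection-alone rate 21% (8.0, 8.1). Stated detection limit 15% (8.1). Primary power 80% at a true 6%, α = 0.05 (8.1).

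**1. Fisher test of x/50 against 0/46.** All x events fall in the partial breast group, so the one-sided p-value is C(50,x)/C(96,x). For 2 ≤ x ≤ 6 the two-sided p-value adds the opposite extreme, C(46,x)/C(96,x).

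| x/50 | One-sided p | Two-sided p |
|---|---|---|
| 3 (6%) | 19,600/142,880 = 0.137 | 34,780/142,880 = 0.243 |
| 4 (8%) | 230,300/3,321,960 = 0.069 | 393,485/3,321,960 = 0.118 |
| 5 (10%) | 2,118,760/61,124,064 = 0.035 | 3,489,514/61,124,064 = 0.057 |
| 6 (12%) | 15,890,700/927,048,304 = 0.017 | 25,257,519/927,048,304 = 0.027 |

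At two-sided 0.05 the largest non-significant count is 5/50. At one-sided 0.05 it is 4/50.

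**2. Reproducing the plan's 15%.** The control is fixed at 0/46, so power is P(X ≥ cutoff) with X binomial(50, p). At p = 0.15:
- Two-sided 0.05: P(X ≥ 6) = 78.1%, close to the 80% used for the primary test.
- One-sided 0.05: P(X ≥ 5) = 88.8%.
- α = 0.5 as printed, two-sided: significance would begin at 2/50 (p = 0.496), which does not fit 15%.

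The primary calculation points the same way. The two-sided 0.05 rule of 4 or fewer events has power 82.1% at a true 6%; the one-sided rule of 5 or fewer has 92.2%. I therefore take two-sided 0.05 as intended and the 0.5 as a slip.

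**3. Chance of a non-significant Fisher result.**

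| True rate | Two-sided, P(X ≤ 5) | One-sided, P(X ≤ 4) |
|---|---|---|
| 5% | 96.2% | 89.6% |
| 8% | 79.2% | 62.9% |
| 10% | 61.6% | 43.1% |
| 12% | 43.5% | 26.8% |
| 15% | 21.9% | 11.2% |

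**4. What each result would allow.** The third column is the two-sided exact binomial test against 21%. The last is the Newcombe 95% interval for the difference from 0/46.

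| x/50 | Fisher p | p against 21% | Exact 95% CI for the rate | Difference, points |
|---|---|---|---|---|
| 2 | 0.496 | 0.001 | 0.5% to 13.7% | −4.2 to +13.5 |
| 3 | 0.243 | 0.008 | 1.3% to 16.5% | −2.7 to +16.2 |
| 4 | 0.118 | 0.023 | 2.2% to 19.2% | −1.1 to +18.8 |
| 5 | 0.057 | 0.057 | 3.3% to 21.8% | +0.4 to +21.4 |

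At 3/50 and 4/50 both tests fall the favourable way while an excess of 16.2 or 18.8 points is not excluded. At a true rate of 8%, one of these two counts is observed with probability 40%.

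At 5/50 the Newcombe interval excludes zero although the Fisher test is non-significant, so an interval and a p-value reported together can disagree unless the plan says which governs.

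Even 0/50 leaves an upper limit of 7.1 points.

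**The case against.** **The plan claims no equivalence.** This stands. The objective is only to compare, section 1.0 says likely, and section 9.0 says if. A reader might infer that the plan treats a non-significant result as showing no difference, but no text says so. The fault is a mismatch between hypothesis and test, with the reading left open.

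**The limitation is disclosed.** This also stands. The 15% figure tells the reader that smaller excesses may be missed. It does not say what a non-significant result would then mean.

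**The interval is largely there already.** Section 8.1 plans an exact interval for the rate, and its upper limit nearly equals that for the difference: 16.5% against 16.2 points at 3/50, 19.2% against 18.8 at 4/50. So the uncertainty will not be hidden. What is missing is its use in the comparison and a rule for interpretation.

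**The extreme case is not a success.** A reader might infer that 5/50 could be reported as good on both comparators. It could not: p = 0.057 against 21% fails the primary test. Of the counts discussed here, 3/50 and 4/50 are the troublesome ones.

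**The 5% figure.** A reader might infer that 3/50 or 4/50 misses the plan's own criterion, or that 2/50 or fewer should be the test of similarity. Section 8.0 says a clinically meaningful improvement "would be an in-breast recurrence rate of 5 percent or less", directly after giving the 21% resection-alone rate. That is a benchmark for improvement over resection alone. It is neither a similarity margin against whole breast radiation nor a limit on the observed count. Section 8.1 powers the primary test at 6%, which is exactly 3/50. A cutoff of 2/50 would also leave an excess of up to 13.5 points open, so it would not establish similarity.

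**Conclusion.** The concern holds as a mismatch in a secondary analysis. The Fisher test against 0/46 cannot support the hypothesis in sections 1.0 and 9.0, and a true rate of 10% would give a non-significant result 62% of the time. Results of 3/50 or 4/50 would look favourable on both comparators while remaining compatible with an excess of about 16 to 19 points.

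The figures assume two-sided α = 0.05, which fits both of the plan's stated operating figures, all 50 patients in the denominator, and the control held at 0/46. With a one-sided test the cutoff drops to 4/50 and the conclusion is the same. The primary test against 21% is unaffected. I class this as a cheap improvement: the documents do not support the stronger charge that the plan asserts equivalence or conceals its detection limit.

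**What to change.** Amend section 8.1 as follows:

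- Report the secondary result as the risk difference from 0/46 with a 95% confidence interval, by a method named in advance. Keep the Fisher p-value as supportive.
- State which of the two governs if they disagree, as Newcombe and Fisher do at 5/50.
- State that a non-significant Fisher test will not be read as similar efficacy, and that any statement about similarity must quote the upper confidence limit of the difference.
- State that, because no margin is specified, the comparison with DMS 9801 is descriptive.
- In the same edit, correct the α of 0.5 and state the sidedness of the test.

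This costs a few sentences and one extra interval, with no added patients or data and no change to the primary test. The downside is that a claim of similar efficacy becomes harder to make: even no recurrences in 50 patients would have to be reported with an upper limit of about 7 points.
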